APPENDIX VIII. Interim Analyses using Bayesian Rules

A.1 Overall Trial Design

The pick-the-winner design includes the following three analyses (displayed in schematic below)

- Perform interim analyses after 60 and 81 patients have been treated and evaluated. The goal of these analyses will be to drop an inferior arm, if indicated, as well as to review the toxicities
- Perform the final analysis after 105 patients have been treated and evaluated, with one exception:
 - if an arm is dropped as inferior after 60 patients, then the remaining 2 arms will be analyzed and compared after 35 patients are evaluable in those arms. If the results are clear-cut, and one arm is superior, then the trial will stop; otherwise accrual will continue until 104 patients (42 in the 2 remaining arms) are randomized and evaluated.

A.2 Methods Used for Establishing the (Bayesian) Rules for Dropping the Inferior Arm or Selecting the Superior Arm

A.2.1 Notation and Distributions:

At any given time in the trial,

- let X_A , X_B , and X_C represent the number of responders observed for regimens A (=MIBG alone), B (=MIBG + vincristine + irinotecan), and C (MIBG + Vorinostat), respectively,
- let n_A , n_B , and n_C represent the total number of patients evaluated for response in arms A, B, and C, respectively,
- and let p_A , p_B , p_C denote the (true) probability of response (i.e. response rates) for regimens A, B, and C.

Thus X_A , X_B , and X_C are binomial random variables with parameters p_A , p_B , p_C , and n_A , n_B , and n_C .
NANT 2011-01 Version Amendment #8 01-10-2018 120

The Bayesian methodology says that p_A , p_B , p_C are not fixed numbers, but rather have a distribution, or range of possible values. So we modeled these distributions as beta with parameters α and β . For our calculations, we will assign the same mean value of 0.20 for all three distributions – but with very little confidence. So for each p (which will be the same for each p_A , p_B , p_C , separately)

$$p \approx \text{Beta}(\alpha, \beta)$$

where $\alpha/(\alpha+\beta)=0.20$ is the mean of the distribution and $\alpha+\beta=1.0$ is like the “sample size”.

We call this our prior distribution of p and p_A , p_B , p_C .

As we observe data (X responders out of n patients treated on each arm separately) then we incorporate these data into our distributions of the true response rate, p . We calculate a new distribution which incorporates both our prior belief (or assumptions) and the data we have observed. So now, after having some data, we have the following distribution for p :

$$p|X \approx \text{Beta}(\alpha + X, \beta + (n-X))$$

where the mean becomes $(\alpha+X)/((\alpha+X)+(\beta+(n-X))) = c[X/n] + (1-c)[\alpha/(\alpha+\beta)]$

and where $c=n/(\alpha+\beta+n)$ and the effective sample size is $\alpha+\beta+n = n+1$.

We call this our posterior distribution of p .

Since the data in the 3 arms of the study are independent and since we know the posterior distributions for each of the response probabilities, then it is easy to determine the posterior probabilities. For this design, instead of calculating the posterior probabilities, we simulated the distributions with 2,000 realizations for each comparison.

A.2.2 Dropping an Arm / Deciding that the Response Rate is Inferior

After 60 patients (and again after 81 patients, if necessary) we will determine:

- (a) $\Pr \{ p_B - p_A > 0.05 \mid X_A, X_B, n_A, n_B \}$ and $\Pr \{ p_C - p_A > 0.05 \mid X_A, X_C, n_A, n_C \}$ and
- (b) $\Pr \{ p_C - p_B > 0.05 \mid X_C, X_B, n_C, n_B \}$ and $\Pr \{ p_A - p_B > 0.05 \mid X_A, X_B, n_A, n_B \}$ and
- (c) $\Pr \{ p_B - p_C > 0.05 \mid X_C, X_B, n_C, n_B \}$ and $\Pr \{ p_A - p_C > 0.05 \mid X_A, X_C, n_A, n_C \}$.

If the 2 probabilities on any line above are both > 0.85 , then we will conclude that Arm A (based on line (a)) or Arm B (based on line (b)) or Arm C (based on line (c)) is inferior and based on this and other considerations, we will close this arm to future randomization. These probabilities were determined based on 2,000 simulations.

A.2.3 Deciding after 90 Patients that we have Sufficiently Strong Data to Stop and Pick the Best Regimen

If an arm is dropped after 60 patients, then we will compare the 2 remaining arms after each has 35 evaluable patients. Without loss of generality, we will assume that Arm A has been dropped. At that time, we will determine the posterior probabilities (where $n_C = n_B = 35$):

$$\Pr \{ p_C - p_B > 0.05 \mid X_C, X_B, n_C, n_B \} \quad \text{and} \quad \Pr \{ p_B - p_C > 0.05 \mid X_C, X_B, n_C, n_B \}$$

If either of these probabilities is > 0.90 , then we will close accrual and declare “a winner”. If not the study will continue until 104 patients have been randomized and are evaluable. These probabilities were also determined based on 2,000 simulations.

A.3 Evaluating the Characteristics (Statistical Properties) of the Proposed Design

The decision to evaluate data at 60 and 81 patients for the possibility of dropping an inferior arm and at 90 patients to select a superior arm early was based on logistic and practical reasons as well as

preliminary simulations. The choice of the values of 0.05, 0.85 and 0.90 for making the decisions was also based on preliminary simulations.

To evaluate the performance of the proposed design, we considered a range of “true” fixed values of p_A , p_B , p_C . For convenience we always set the value of p_A to be the lowest response rate and the value of p_C to be the highest response rate. For each configuration of (p_A, p_B, p_C) , we generated 2,500 trials of 105 patients and evaluated the following design characteristics: probability of correctly selecting the best arm, probability of dropping the inferior arm, probability of dropping the best arm, average number of patients in the inferior arm. The results are summarized in Table A below.

Response Rate in Inferior & Middle Arms		Probability of Correctly Selecting Best Arm			Probability of Dropping Inferior Arm			Probability of Dropping Best Arm			Average # of Patients in the Inferior Arm		
		Difference in Response Rate between Middle & Best Arms			Difference in Response Rate between Middle & Best Arms			Difference in Response Rate between Middle & Best Arms			Difference in Response Rate between Middle & Best Arms		
Inferior	Middle	+0.10	+0.15	+0.20	+0.10	+0.15	+0.20	+0.10	+0.15	+0.20	+0.10	+0.15	+0.20
0.10	0.10	87%	94%	98%	21%**	25%	26%	0.4%	0.1%	0.0%	.	.	.
0.15	0.15	81%	92%	97%	25%	26%	30%	0.4%	0.4%	<0.1%	.	.	.
0.20	0.20	78%	90%	96%	25%	29%	32%	1.2%	0.5%	0.3%	.	.	.
0.25	0.25	76%	88%	96%	28%	32%	35%	1.4%	0.6%	0.1%	.	.	.
0.30	0.30	76%	86%	95%	27%	32%	34%	1.5%	0.5%	0.2%	.	.	.
0.35	0.35	73%	88%	94%	28%	30%	34%	1.4%	0.6%	<0.1%	.	.	.
0.05	0.15	88%	96%	99%	50%	51%	52%	0.0%	0.0%	0.0%	28	28	28
0.10	0.20	88%	95%	98%	44%	48%	50%	0.2%	0.1%	0.0%	29	28	28
0.15	0.25	85%	94%	98%	41%	43%	48%	0.3%	0.2%	0.0%	30	29	29
0.20	0.30	85%	92%	97%	41%	45%	46%	0.4%	0.1%	0.0%	30	29	29
0.25	0.35	82%	92%	96%	38%	45%	43%	0.4%	0.0%	<0.1%	30	29	30
0.05	0.20	89%	95%	98%	69%	71%	72%	<0.1%	<0.1%	0.0%	26	25	25
0.10	0.25	86%	92%	98%	60%	65%	68%	0.0%	0.1%	0.0%	27	26	26
0.15	0.30	84%	93%	97%	61%	62%	64%	0.1%	0.0%	0.1%	27	27	26
0.20	0.35	85%	93%	97%	57%	60%	61%	0.2%	0.1%	0.0%	28	27	27
0.25	0.40	83%	93%	97%	56%	60%	62%	0.1%	<0.1%	0.0%	28	27	27

* probabilities estimated based on 2,500 simulations and are reported as percents
 ** in this box, for the probability of dropping the inferior arm, the percent reflects dropping either Arm A or Arm B (since their response rates are equal for these 6 lines)

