10.0 STATISTICAL CONSIDERATIONS

10.1 Pick-the-Winner Design

Up to a total of 105 eligible and evaluable patients will be randomly assigned to one of the 3 MIBG arms. At completion of the study, the regimen with the highest observed response rate (by central review of response) after one course of therapy will be selected as the “winner” – i.e. the regimen that will be recommended as the MIBG backbone for future studies – provided that toxicity, tolerability, and other considerations confirm the feasibility of the regimen.

Two interim analyses for futility (to drop an inferior arm) will be undertaken: after 60 patients (approximately 20/arm) and after 81 patients (approximately 27/arm) have been randomized and completed at least one course and deemed evaluable for response. This analysis will be performed initially using site report of response. The following rule will be applied: if one of the arms is clearly inferior to the other two, then consideration will be given to dropping that single regimen. Study accrual will not pause while awaiting the results of any interim analysis (see below for modification per Amendment 7A). However, study accrual will be halted if needed to complete central review of response prior to dropping any regimen. The criterion to be used is based on Bayesian posterior probabilities (see Appendix VIII).

In addition, if one arm is dropped at the time of the 1st interim analysis, then after 35 patients have been randomized to each of the remaining arms and evaluated after the 1st course, we will compare these 2 remaining arms based on site report of response. If one arm is not clearly superior according to Bayesian posterior probabilities, accrual will continue until 42 evaluable patients per remaining arm have been randomized (yielding total sample of 104 patients in this scenario).

If neither futility rule is met, accrual will continue until 35 patients/arm are eligible and evaluable, for a total of 105 patients. With Amendment 7A, the design was modified to apply stochastic curtailment principles to permit early selection of a winner (see below). In order to account for potentially ineligible or inevaluable patients, a maximum of 115 patients are anticipated to enroll to yield 105 eligible and evaluable patients.

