The table below summarizes the minimal impact of incorporating stochastic curtailment at this stage, on the overall probability of correct selection, for a variety of scenarios (in none of these scenarios is the probability of correct selection decreased).

Table: Probability* of Selecting the Correct Arm						
True Probability of Response for the 2 Inferior Arms	Without Stochastic Curtailment			With Stochastic Curtailment		
	Difference in True Probability of Response between Best Arm and the Other 2 (least favorable configuration)			Difference in True Probability of Response between Best Arm and the Other 2 (least favorable configuration)		
	+0.0	+0.05	+0.10	+0.0	+0.05	+0.10
0.10	1.00	0.676	0.855	1.00	0.705	0.875
0.15	1.00	0.627	0.818	1.00	0.658	0.827
0.20	1.00	0.599	0.780	1.00	0.622	0.814
0.25	1.00	0.592	0.770	1.00	0.608	0.788
0.30	1.00	0.583	0.736	1.00	0.607	0.777

*Probabilities of correct selection estimated by simulation, using same methods a results in the Appendix

Logistic Considerations for 2nd Interim Analysis: Study accrual will pause while awaiting the results of the 2nd interim analysis, until it is clear that 81 patients are “evaluable for response”. In addition, no final decision will be made to terminate accrual or drop an arm, until central review of response is completed.

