10.5 Sample Size and Study Duration

While we expect that both the vincristine/irinotecan and the vorinostat arms will demonstrate higher response rates compared to the MIBG-alone arm – and that the selection therefore will only involve those

two arms – we have included the MIBG-alone arm to calibrate the improvement and better understand the impact of these chemotherapy additions. However, for purposes of determining the number of required patients, we will consider that all three arms are candidates of selection (i.e. could result in the highest observed response rate). The number of patients (35 per MIBG regimen, if no arms are dropped as inferior) was calculated to ensure an 80% chance that the regimen with the highest response rate is selected – if in fact that response rate is at least 15% better than the other two (using the methods described by Sobel and Huyett¹¹⁴ and summarized by Bechhofer, Santner and Goldsman¹¹⁵). Because we have incorporated Bayesian criteria for dropping an inferior arm or stopping early, the power of correct selection and other design characteristics were determined by simulation (see Appendix VIII for more details).

Table A in Appendix VIII summarizes the probability of correct selection, the probability of dropping one arm for futility, the probability of dropping the superior arm for futility, and the average number of patients in the inferior arm.

Estimates of the number of available patients for this study are derived from previous ¹³¹I-MIBG studies at NANT ¹³¹I-MIBG institutions. Specifically, NANT01-02 accrued 50 patients with refractory disease over approximately 40 months of active patient recruitment. NANT04-06 accrued 26 patients with relapsed or refractory disease over the approximately 40 months during which that study was open. This accrual rate underestimates the number of available patients given that NANT04-06 was a phase I study that utilized a 3+3 dose escalation strategy and accrual was closed for a minimum of 6 weeks after the third patient at each dose level was treated. CHOP, Cincinnati Children's, UCSF, and the University of Michigan treat 25, 12, 12, and 7 patients per year on their respective expanded access ¹³¹I-MIBG protocols. Newer NANT MIBG centers now include Children's Hospital Boston, Cook Children's Hospital, Children's Hospital of Colorado, Hospital for Sick Children, and Seattle Children's Hospital. These newer centers will increase access to MIBG treatment slots.

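### Table A overstates by 9 to 16 points how often the written 0.85 rule drops an inferior arm; its selection figures count ties as correct, and the tabulated curtailment gains do not reproduce

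*Combined protocol and SAP*

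**What the plan says.** Appendix VIII specifies the interim rule completely. The prior is a beta distribution with weight 1, and "we will assign the same mean value of 0.20 for all three distributions". At 60 and 81 patients, A.2.2 compares each arm with the other two through the posterior probability of a difference above 0.05: "If the 2 probabilities on any line above are both > 0.85", the arm is judged inferior. A.3 repeats the constants: "The choice of the values of 0.05, 0.85 and 0.90 for making the decisions was also based on preliminary simulations". Table A follows as the result, for each configuration of true rates: "we generated 2,500 trials of 105 patients and evaluated the following design characteristics: probability of correctly selecting the best arm".

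Section 10.5 relies on this work: "the power of correct selection and other design characteristics were determined by simulation". It refers the reader to Table A for correct selection, arm dropping and inferior-arm size.

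On the final choice, section 10.1 says "the regimen with the highest observed response rate (by central review of response) after one course of therapy will be selected", subject to toxicity and feasibility. It does not say what happens if two arms tie.

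Section 10.1.1 (Amendment 7A) adds stochastic curtailment at 81 patients and tabulates correct selection with and without it, remarking that "in none of these scenarios is the probability of correct selection decreased".

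**The concern.** The rule is specified closely enough to be coded without guesswork, so Table A should reproduce within simulation error. It does not. A reader of section 10.5 would expect a poor arm to be shed roughly 1.2 to 2 times as often as the written rule sheds it (69/57.3 = 1.2; 21/10.4 = 2.0).

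Two further columns raise questions. If ties are frequent, how they are scored affects correct selection, and the plan does not state a convention. It is also surprising that stopping early on less information should improve selection in every non-trivial scenario.

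At stake is whether the published operating characteristics describe the design being run, in particular at the 81-patient look, where both the 0.85 rule and the curtailment rule apply.

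**Working it through.** **Inputs.** Prior Beta(0.2, 0.8), from mean 0.20 and weight 1 (A.2.1). Margin 0.05 and cut-off 0.85 (A.2.2). Looks at 20 and 27 per arm (10.1). After a drop at 60, the two remaining arms are compared at 35 each with cut-off 0.90, and otherwise extended to 42 each (A.1, A.2.3). With no drop, the final analysis is at 35 per arm. One assumption: if an arm is dropped at 81, the other two share the remainder of 105, so (105 − 27)/2 = 39 each.

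**Rule.** With X responders among n, p | X ~ Beta(0.2 + X, 0.8 + n − X). For arms j and k, Pr(p_k − p_j > 0.05) = ∫ f_j(u)[1 − F_k(u + 0.05)] du. Arm j is dropped if this exceeds 0.85 against both other arms. I evaluated the integral numerically and simulated 200,000 trials per Table A cell.

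**Precision of the plan's figures.** At 2,500 trials the standard error is at most √(0.5 × 0.5/2500) = 1.0 point.

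**(a) Probability of dropping the inferior arm**

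| True rates (inferior/middle/best) | Table A | Written rule | Gap (points) |
|---|---|---|---|
| 0.10/0.10/0.20 | 21% | 10.4% | 10.6 |
| 0.05/0.15/0.25 | 50% | 34.4% | 15.6 |
| 0.25/0.35/0.45 | 38% | 28.6% | 9.4 |
| 0.05/0.20/0.30 | 69% | 57.3% | 11.7 |
| 0.25/0.40/0.60 | 62% | 47.2% | 14.8 |

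Over all 48 cells the gap is 9.4 to 15.6 points, always in the same direction. Using the plan's own 2,500 trials and 2,000 posterior draws gives 10.0%, 33.8%, 26.2% and 44.8% for rows 1, 2, 3 and 5, so posterior sampling noise is not the cause. Unequal allocation, flatter priors and a third look at 35 per arm do not close the gap either.

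The other columns move consistently. Mean inferior-arm size is 28 stated against 30.6 at 0.05/0.15/0.25, and the gap is 0.7 to 2.6 patients over the 30 cells reported. A bound shows why 28 cannot arise there under the written rule: even if every drop came at the first look, the mean would be at least 35 − 15 × 0.344 = 29.8. With the stated 50%, the same bound is 35 − 15 × 0.50 = 27.5, which allows 28. Dropping the best arm is overstated: 1.2% against 0.4% at 0.20/0.20/0.30, and 1.5% against 0.7% at 0.30/0.30/0.40.

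A cut-off in the region of 0.75 to 0.77 fits the drop column far better (root-mean-square misfit 2.0 points at 0.75, against 12.1 at 0.85). This is inference only; some cells still miss by 3 to 4 points.

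**(b) Ties**

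| Cell | Stated | Ties correct | Ties split at random |
|---|---|---|---|
| Table A, 0.10/0.10/0.20 | 87% | 85.9% | 81.0% |
| 10.1.1 without curtailment, 0.10, +0.05 | 0.676 | 0.683 | 0.607 |

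With ties scored as correct, the Table A selection figures reproduce within about 2 points. Against random tie-breaking they are too high by up to 6.0 points at +0.10, 4.4 at +0.15 and 2.3 at +0.20. The 10.1.1 without-curtailment figures are about 3 to 7 points too high on that basis. Ties for first occur in about 10% of trials at +0.10 in the six equal-arm rows, 6–7% in the other ten rows, and 13–17% at +0.05.

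**(c) Curtailment.** I stopped at 27 per arm when the exact conditional probability of the leader staying highest exceeded 0.90 under every equal-rate scenario from 0.10 to 0.25. Ties are scored as correct; 200,000 trials per cell.

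| Lower rate, difference | Stated without → with | Re-run without → with |
|---|---|---|
| 0.10, +0.05 | 0.676 → 0.705 | 0.683 → 0.682 |
| 0.15, +0.05 | 0.627 → 0.658 | 0.637 → 0.635 |
| 0.20, +0.10 | 0.780 → 0.814 | 0.785 → 0.782 |
| 0.25, +0.10 | 0.770 → 0.788 | 0.767 → 0.763 |
| 0.30, +0.10 | 0.736 → 0.777 | 0.752 → 0.748 |

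Over the ten non-trivial cells the stated gain is 0.9 to 4.1 points. The re-run change lies between about −0.5 and +0.2 across repeated runs. Stated with-curtailment values exceed the re-run by 1.3 to 3.2 points in all ten cells. Against 2,500-trial error, chi-square on 10 degrees of freedom is about 71 for that column and 7.7 for the without column. Counting a tie as still highest makes the change −1.7 to −0.7 points, further from the stated gains.

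**Headline target.** At 35 per arm and a 15-point difference, with no interim rule, the lowest correct-selection probability over all rates is 82.6% with random ties, 85.9% with ties correct and 79.4% with ties wrong. The lowest Table A cell at +0.15, with the interim rules and random ties, is 83.6%.

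**The case against.** Part (a) has no good answer on the arithmetic. The best defence is that it matters little: dropping is discretionary under 10.1 and A.2.2, the first look has passed with no arm dropped, the second look uses the explicit formulas rather than Table A, and the written rule loses the best arm less often than advertised. All of that stands and limits the consequence.

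On (b), counting ties as correct is a scoring convention, not a miscalculation. The 10.1.1 table scores equal arms as 1.00, and final selection also weighs toxicity and feasibility. Random tie-breaking is not prescribed either. That is fair. What remains is that the convention is unstated, that a tie does not identify a single regimen, and that the choice moves the figures by several points.

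On (c), section 10.1.1 gives no trial count, its highlighted cells cannot be seen in the text available, and it does not say how curtailment combines with an arm drop. If the two columns are independent runs of 2,500, each gain has a standard error of about 1.0 to 1.4 points, and five of the ten are individually below 1.96 standard errors. This weakens any single cell. It does not explain ten gains in the same direction, and no variant I tried (drop cut-offs of 0.75 or 0.775, no dropping) produces them. The section's wider statement that the impact is minimal is supported.

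**Conclusion.** The concern holds. Table A does not describe the written 0.85 rule: inferior-arm drop probabilities are 9 to 16 points too high, inferior-arm sizes 0.7 to 2.6 patients too small, and best-arm drop risk too high where it is not negligible. The selection figures depend on an unstated convention that ties are correct. The with-curtailment gains are not explained by the written rule.

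The drop result rests on equal allocation at the looks and the stated prior; the curtailment result also rests on my reading of the scenarios. The simulation code is not in the documents, so the cause is unknown. A looser simulated cut-off is plausible but unproven.

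The effect is bounded: the 80% target at a 15-point difference survives random tie-breaking, the sample size is unaffected, and no interim decision is computed from Table A. It should be corrected because section 10.5 cites these figures as the design's properties.

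**What to change.** Re-run Table A and the 10.1.1 table with the rules as written (0.05, 0.85, 0.90). Restate all four Table A columns and both 10.1.1 column groups, giving the number of simulated trials and how curtailment and arm dropping interact.

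If the records show that another cut-off was simulated, say so and make A.2.2, A.3 and Table A agree. That is a reason to correct the table, not to loosen the 0.85 rule after the first interim results have been seen.

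Add one sentence to 10.1 pre-specifying a tie rule of the sponsor's choice, use it in the simulation, and report three outcomes separately: best arm uniquely highest, best arm tied for highest, and wrong arm selected.

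The cost is a few hours of simulation, two restated tables and one sentence. Selection and inferior-arm figures become less favourable, the best-arm-drop figure more favourable, and the sample size does not change.
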